5.1.2 Trial Medication Administration and Schedule

Subjects will receive IV infusion of MSB0011359C over 1 hour (-10 minutes / +20 minutes, that is, over 50 to 80 minutes) once every 2 weeks. Subjects enrolled in the 30 mg/kg and 2400 mg flat-dose cohorts may have a total infusion time of up to 120 minutes. In order to mitigate potential infusion-related reactions, premedication with an antihistamine and with paracetamol (acetaminophen) (for example, 25-50 mg diphenhydramine and 500-650 mg paracetamol [acetaminophen] IV or oral equivalent) approximately 30 to 60 minutes prior to each dose of MSB0011359C is mandatory for the first 2 infusions and is optional and at the discretion of the Investigator after the second infusion (premedication is optional for all infusions for subjects in the NSCLC biomarker cohort being treated at the US NCI). If Grade ≥ 2 infusion reactions are seen during the first two infusions, premedication should not be stopped. Steroids as premedication are not permitted.

The trial treatment schedules are provided in the Schedules of Assessments (see [Table 1](#) and [Table 2](#)).

The formulation and packaging information of MSB0011359C is provided in Sections 6.1 and 6.6.

5.1.3 MSB0011359C Dose Escalation

The dose-escalation part of the trial is expected to enroll between 3 and 82 subjects. Eligible subjects will be patients with metastatic or locally advanced solid tumors who have failed standard therapies or who have no standard effective therapy available.

5.1.3.1 Starting Dose

The starting dose of MSB0011359C will be 1 mg/kg.

5.1.3.2 Dose Escalation

The dose escalation will use a standard 3 + 3 scheme with the following planned doses (once every 2 weeks):

- 1 mg/kg
- 3 mg/kg
- 10 mg/kg
- 20 mg/kg
- 30 mg/kg
- 2400 mg flat dose

The DLT period is defined as 21 days after the start of therapy. The first subject of each cohort will be observed for at least 5 days before the second subject can be treated. Thereafter, within each cohort 48 hours must pass before a new subject can initiate dosing. Once the 3 or 6 subjects have passed the 21-day DLT evaluation period the SMC will review the safety and available PK data to decide upon further dose escalation. Pharmacokinetic data from the previous cohort will be required for SMC review (for example, when the SMC is reviewing safety data from the 10 mg/kg cohort, available PK data from the 3 mg/kg cohort); however, PK data from the cohort under review will not be required.

The criteria for moving from 1 dose level to another do not allow escalation to the next cohort in cases where ≥ 2 of 3 or 6 subjects in a cohort experience a DLT. If 1 DLT in 3 subjects is observed, this cohort will be automatically expanded to 6 subjects with SMC meeting after the 6th subject completes the DLT evaluation period. Likewise, if at the highest dose level (30 mg/kg) no DLTs occurred in the first 3 subjects, the cohort may be expanded to 6 subjects with SMC meeting after the 6th subject completes the DLT evaluation period.

The MTD is defined as the highest dose where fewer than 2 of 6 subjects experience a DLT. Thus, the MTD cohort should accrue a total of 6 subjects. If 1 of 6 subjects has experienced a DLT at a dose below 10 mg/kg, dose escalation will be modified (Table 4).

The DLT criteria will not apply to any of the expansion cohorts.

Table 4 Modification of Dose Escalation Based on DLT Observations

Dose Escalation Schedule Scenarios	Dose of MSB0011359C (mg/kg)	
	No DLT at Dose Level	DLT at Level 1 (1 mg/kg) or DLT at Level 2 (3 mg/kg)
Level 1	1 mg/kg	1
Level 2	3 mg/kg	3
Level 3	10 mg/kg	7 ^a
Level 4	20 mg/kg	10
Level 5	30 mg/kg	20
Level 6	2400 mg	No modification

DLT = dose-limiting toxicity.

a If 1 of 6 subjects has a DLT at dose level 1 or 2.

5.1.3.3 Dose-Limiting Toxicity

A DLT is defined as any Grade ≥ 3 AE assessed as related to the IMP by the Investigator and / or Sponsor (that is, Grade ≥ 3 ADR; grading according to the NCI-Common Terminology Criteria for Adverse Events version v4.03 [CTCAE v4.03]) occurring in the DLT evaluation period (21 days after first administration of MSB0011359C) confirmed by the SMC to be relevant for the IMP treatment. The SMC recognizes that in the absence of prior human experience with MSB0011359C, a conservative approach will be adopted in ascribing the relevance of the treatment-related toxicity to IMP. Treatment-related SAEs will be ascribed as related to drug except where a clear relationship to the underlying disease or recognized comorbidities is evident.

A DLT is specifically defined as the following:

Any Grade ≥ 3 adverse event that is related to MSB0011359C, occurring during the DLT evaluation period (21 days after first administration of MSB0011359C), except for those listed below. Also, elevated alanine aminotransferase (ALT) or aspartate aminotransferase (AST) 3 times the upper limit of normal (ULN) range and a concomitant elevation of bilirubin 2 times the ULN attributable to study drug constitutes a DLT.

- Grade 3 infusion-related reactions resolving within 6 hours from the end of infusion and controlled with medical management.
- Transient (≤ 6 hours) Grade 3 flu-like symptoms or fever, which is controlled with medical management.
- Transient (≤ 24 hours) Grade 3 fatigue, local reactions, headache, nausea, emesis that resolves to Grade ≤ 1 .
- Grade 3 Hgb decrease (< 8.0 g/dL) that resolves to at least 9 g/dL within 14 days or changes in associated red blood cell parameters during such a Hgb decrease that resolve within 14 days without blood transfusion or erythroid growth factor use.
- Malignant skin lesion that is local and can be resected with negative resection margin.

Dose-limiting toxicities that require treatment discontinuation are described in Section 5.1.7.2.

Subjects who do not complete the DLT observation period for reasons other than a DLT will be replaced.

5.1.4 Expansion Cohorts

After an MSB0011359C dose for further investigation is established, enrollment of several expansion cohorts will be opened to determine the safety and clinical activity of MSB0011359C in specific indications (see Section 3.4.2 for details).

Following safety and PK analysis of the escalation cohorts, a flat dose of 1200 mg/infusion was chosen for all expansion cohorts, except for the NSCLC second-line cohort, in which 40 subjects will receive 500 mg/infusion and 40 subjects will receive 1200 mg/infusion.

5.1.5 Planned Number of Subjects

The planned number of the evaluable subjects for this trial is derived from the dose-escalation “3 + 3” design and the expansion cohort sizes:

- Dose-escalation phase: 3 to 82 subjects.
- Expansion cohorts: Up to approximately 566 subjects.

The final sample size, however, may vary depending on the total number of dose levels to be escalated and tested, and the subject replacement for DLT evaluations if applicable.

In the event that rapid recruitment in the expansion phase impacts supply of IMP, the screening of new subjects for any cohort may be temporarily paused with 24 hours’ notice to Investigators.

5.1.6 Planned Treatment Duration

The trial duration for a subject is estimated to be up to 2 years. This includes a 28-day Screening period (decision will be made in this period for subjects’ trial inclusion if all eligibility criteria are met), a treatment duration until confirmed PD, unacceptable toxicity, or any criterion for withdrawal from the trial or IMP occurs (see Section 5.5) and a 28-Day Safety Follow-up visit 4 weeks after the last dose of MSB0011359C administration.

Subjects who have experienced SD, PR, or CR should continue treatment through the end of 12 months, although additional treatment is possible. If the Investigator believes that a subject may benefit from treatment beyond 12 months, it may be permissible after discussion with the Medical Monitor and the Sponsor Medical Responsible. In the case of PD, subjects should continue treatment through their next tumor assessment, if they meet the criteria described in Section 5.5.1.

For subjects who achieve SD, a PR or CR on MSB0011359C therapy and then subsequently develop disease progression after stopping therapy, but prior to the end of the trial, 1 re-initiation course of treatment at the same dose and schedule and treatment duration up to 12 months is

allowed at the discretion of the Investigator and agreement of the trial Medical Responsible. A discussion between the Investigator and Sponsor should take place. The Investigator will need to confirm that the benefit of re-initiating treatment outweighs any risk involved, such as that which led to initial treatment discontinuation. Moreover, for subjects in which BOR was SD, the Investigator should confirm no other reasonable treatment options are available. In order to be eligible for retreatment, the subject must not have experienced any toxicity that led to permanent treatment discontinuation of the initial MSB0011359C therapy, unless the toxicity is deemed to be manageable and the potential benefit outweighs the risk of re-exposure. Prior to re-initiation of the trial treatment, malignant disease needs to be radiologically re-staged to assess all known sites of the disease and to establish a new baseline for subsequent tumor measurements. Relevant safety laboratory results must be available and verified prior to re-initiating of treatment. Subjects who re-initiate treatment will stay on trial and will be treated and monitored according to the Schedules of Assessment for the Expansion portion of the trial starting at Week 1, Day 1 (see [Table 2](#)).

Moreover, any ADRs should be followed until they resolve, return to Baseline, or are irreversible (see [Section 7.1.4](#) for details).

Planned first subject in: Q3, 2015.

Planned date last subject out (dose escalation, including follow-up): Q3, 2019.

Planned date last subject out (after expansion and follow-up): Q4, 2021.

5.1.7 Dose Modification and ADRs Requiring Treatment Discontinuation

5.1.7.1 Dose Modification

For the dose-escalation cohorts (except for the 2400 mg flat-dose cohort), the dose of MSB0011359C will be calculated based on the weight of the subject determined on the day prior to or the day of each drug administration.

Each subject will stay on the MSB0011359C dose level assigned in the trial unless treatment needs to be stopped. Dosing modifications (changes in infusion rate) and dose delays are described in [Sections 5.1.7.2](#) and [6.5.4](#) and subsections. There are no dose reductions.

5.1.7.2 Adverse Drug Reactions Requiring Treatment Discontinuation

Certain ADRs, defined as an AE assessed as related to MSB0011359C by the Investigator and / or Sponsor, may require permanent treatment discontinuation of MSB0011359C (listed below). For certain ADRs assessed to be immune-related, [Table 7](#) criteria may supersede this section. These criteria may allow the subject to continue on study if medically indicated after consultation with Medical Monitor.

Any Grade 4 ADRs require permanent treatment discontinuation except for single laboratory values out of normal range that do not have any clinical correlate and resolve to Grade \leq 1 or Baseline grade within 7 days with adequate medical management.

Any Grade 3 ADRs require treatment discontinuation except for any of the following:

- Transient (\leq 6 hours) Grade 3 flu-like symptoms or fever, which is controlled with medical management.
- Transient (\leq 24 hours) Grade 3 fatigue, local reactions, headache, nausea, emesis that resolves to \leq Grade 1 or Baseline grade.
- Tumor flare phenomenon defined as local pain, irritation, or rash localized at sites of known or suspected tumor.
- Any Grade \geq 3 drug-related amylase or lipase abnormality that is not associated with symptoms or clinical manifestations of pancreatitis. The Study Medical Monitor should be consulted for such Grade \geq 3 amylase or lipase abnormalities. If the amylase or lipase abnormality not associated with symptoms or clinical manifestations of pancreatitis has not resolved to Grade \leq 1 within the subsequent 2 cycles (28 days), the subject should permanently discontinue treatment with MSB0011359C unless approved to continue by Medical Monitor after specific request from site Investigator.
- Grade 3 Hgb decrease ($<$ 8.0 g/dL) that is clinically manageable with blood transfusions or erythroid growth factor use does not require treatment discontinuation. During the 21-Day-DLT period, a Grade 3 Hgb decrease ($<$ 8.0 g/dL) requires treatment discontinuation, unless it resolves to at least 9 g/dL within 14 days or changes in associated red blood cell parameters during such a Hgb decrease that resolve within 14 days without blood transfusion or erythroid growth factor use.
- Increases in Eastern Cooperative Oncology Group performance status (ECOG PS) \geq 3 that resolves to \leq 2 by Day 1 of the next cycle (infusions should not be given if the ECOG PS is \geq 3 on the day of IMP administration and should be delayed until ECOG PS \leq 2).
- Keratoacanthoma and squamous cell carcinoma of the skin. Any suspicious skin lesion should be biopsied and be surgically removed. The Study Medical Monitor should be consulted.
- Grade 3 or 4 dermatological irAEs, treatment should be delayed and treatment started according to [Table 7](#), if condition improves to Grade 1, treatment may be resumed. If \geq 2 consecutive doses are missed, the Medical Monitor should be consulted.
- Grade 3 or 4 symptomatic endocrinopathies (eg, thyroiditis or hypophysitis), treatment should be delayed and treatment started according to [Table 7](#), if condition improves to Grade 1, treatment may be resumed. If \geq 2 consecutive doses are missed, the Medical Monitor should be consulted.
- Other immune-related ADRs, see [Table 7](#).

Any Grade 2 ADR should be managed as follows:

- If a Grade 2 ADR resolves to Grade \leq 1 by the last day of the current cycle, treatment may continue.

- If a Grade 2 ADR does not resolve to Grade ≤ 1 by the last day of the current cycle but it is manageable and / or not clinically relevant, the ADR should be discussed with the Medical Monitor and based upon discussion it is possible the infusion will be given on the following cycle. If at the end of the following cycle, the event has not resolved to Grade 1, discussion should be had with the Medical Monitor about permanently discontinuing treatment with MSB0011359C.
- Upon the second occurrence of the same Grade 2 ADR in the same subject (except for fatigue and hormone insufficiencies that can be managed by replacement therapy), continuation of treatment with MSB0011359C has to be discussed with the Medical Monitor and might be permanently discontinued.
- Infusion-related reactions and hypersensitivity reactions (Grades 1 to 4) should be handled according to the guidelines provided in Sections 6.5.4.1 and 6.5.4.2, respectively.
- Anemia should be handled according to the guidelines provided in Section 6.5.4.4.
- If immune-related ADR, see Table 7.

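### Section 5.1.7.2 gives two opposing stop rules for a Grade 4 amylase or lipase rise without pancreatitis: a 7-day limit in one sentence, 28 days or longer in a bullet

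*Protocol*

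**What the plan says.** Section 5.1.7.2 of the protocol sets the drug reactions that end treatment. For Grade 4 it says "Any Grade 4 ADRs require permanent treatment discontinuation except for single laboratory values out of normal range". Such a value must have no clinical correlate and must return to Grade 1 or less "or Baseline grade within 7 days with adequate medical management".

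The next rule opens "Any Grade 3 ADRs require treatment discontinuation except for any of the following" and is followed by ten bullets. The fourth concerns any Grade 3 or higher "drug-related amylase or lipase abnormality that is not associated with symptoms or clinical manifestations of pancreatitis". It says that the Medical Monitor should be consulted for these abnormalities, and it repeats the grade label when it does so. If the value is not back to Grade 1 or less "within the subsequent 2 cycles (28 days), the subject should permanently discontinue treatment with MSB0011359C unless approved to continue by Medical Monitor", the latter on a specific request from the site.

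The section also opens with a general clause: for certain immune-related reactions, the Table 7 "criteria may supersede this section".

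**The concern.** A Grade 4 amylase or lipase rise without pancreatitis falls under both texts. It is a Grade 4 drug reaction, so the Grade 4 sentence applies with its 7-day limit. It is also Grade 3 or higher, so the bullet applies with its 28-day limit. The bullet sits under a heading that excuses items from the Grade 3 rule, and nothing there excuses them from the Grade 4 rule.

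This is a stopping rule for patient safety, to be applied at about 220 planned sites (Section 2.1). Two sites could follow the protocol faithfully and treat the same event in opposite ways. The bullet does not require doses to be held meanwhile, so an infusion that one text forbids is one that the other permits. The classification also carries forward. Sections 5.1.6 and 7.1.2 make retreatment depend on whether a toxicity led to permanent discontinuation. Both enzymes are in the full chemistry panel (Table 11), and Section 3.5.2 lists pancreatitis as an important potential immune-related risk.

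**Working it through.** The plan states no figure to reproduce. The check is a comparison of texts plus simple day counts.

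**Inputs**
- Limit in the Grade 4 sentence: 7 days (Section 5.1.7.2).
- Limit in the amylase/lipase bullet: 2 cycles (Section 5.1.7.2).
- Cycle length: 14 days (Section 7.1.2), so 2 × 14 = 28 days, which agrees with the figure in the bullet.
- Dosing interval: 2 weeks.

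**Same event under each text.** Take a Grade 4 drug-related lipase value with no clinical correlate, and assume that both clocks start at onset.

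| Returns to Grade 1 or less | Grade 4 sentence | Bullet |
|---|---|---|
| By day 7 | No stop | No stop |
| Days 8 to 28 | Permanent stop | No stop |
| After day 28 | Permanent stop | Permanent stop, unless the Medical Monitor approves continuing |

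**Length of the conflict.** 28 − 7 = 21 days. With an infusion every 14 days, 21 / 14 = 1.5, so any such span holds at least one scheduled infusion.

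**Sensitivity to the start of the clock.** The protocol does not say that the two periods start together. If the two subsequent cycles are counted from the next cycle start, up to 14 days after onset, the bullet's limit falls as late as 14 + 28 = 42 days after onset. The conflict then lasts up to 42 − 7 = 35 days. The range is therefore about 21 to 35 days, before any extension by the Medical Monitor.

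**Does another text decide?**
- Table 7 (Section 6.5.4.3) has seven organ sections: gastrointestinal, dermatological, pulmonary, hepatic, cardiac, endocrine and renal. None has an amylase, lipase or pancreatic row, so the superseding clause gives no answer.
- Section 5.5.1 withdraws subjects for Grade 3 or higher reactions apart from those that 5.1.7.2 allows, which leads back to the section in conflict.
- Section 6.5.4.8 excuses Grade 3 and 4 laboratory abnormalities without clinical significance, but only from dose interruption and only for events not related to study drug. The events here are related by definition.

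**The case against.** Four arguments favour leaving the text alone.

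*The specific bullet beats the general sentence.* The bullet gives its grade range twice, so its reach to Grade 4 looks deliberate. That is good evidence of intent. It is not decisive, because the Grade 4 exception is specific too: it addresses isolated, clinically silent laboratory values, the class to which this event belongs, and sets its own limit.

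*The Medical Monitor is consulted.* This lowers the chance that a site decides alone. But the consultation belongs to the bullet, and the Grade 4 sentence leaves no discretion.

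*Few enzyme rises become drug reactions.* Section 7.4.1.1 keeps abnormal laboratory findings out of adverse event reporting unless they come with signs or symptoms, lead to discontinuation or are judged medically important. That stands as a limit on how often the conflict arises. It does not remove the conflict, since the Grade 4 sentence itself treats isolated laboratory values as possible drug reactions.

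*The clocks may differ.* Correct, and the 21 days rest on that assumption.

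A reader might also infer a wider contradiction, because two more bullets in the Grade 3 list state Grade 4: "Grade 3 or 4 dermatological irAEs, treatment should be delayed and treatment started according to" Table 7, and "Grade 3 or 4 symptomatic endocrinopathies (eg, thyroiditis or hypophysitis), treatment should be delayed". The documents do not support that. The opening clause lets Table 7 supersede the section for immune-related reactions. Both bullets cite Table 7, and a further bullet sends other immune-related reactions there. Table 7 has a Grade 3 to 4 skin row and a symptomatic endocrinopathy row, and both allow treatment to resume. Read together, these texts already permit resumption. The clause is loosely worded and sits far from the Grade 4 sentence, so a cross-reference would help. A site that misread it would stop treatment too readily, which is the cautious error.

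**Conclusion.** The contradiction is real for one event: a Grade 4 drug-related amylase or lipase abnormality without symptoms or clinical signs of pancreatitis. If both clocks start at onset, the two rules give opposite instructions for recovery on about days 8 to 28, and no other section settles which applies. The comparison assumes that the value has no clinical correlate of any kind, as the Grade 4 exception requires, and that it has been classed as a drug reaction. How often this happens cannot be judged, because the documents give no frequency. No power, alpha, sample size or endpoint is touched. For Grade 4 skin and endocrine events the matter is one of clarity only. The correction is worth making because a permanent-stop rule should give one instruction.

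**What to change.** Choose one rule for the enzymes and write it into Section 5.1.7.2.

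- If 28 days is intended at Grade 4, add to the Grade 4 sentence: *and except amylase or lipase abnormalities without symptoms or clinical manifestations of pancreatitis, which are managed per the bullet below (Medical Monitor to be consulted)*.
- If the 7-day limit is intended at Grade 4, change the grade label in the amylase/lipase bullet from Grade ≥ 3 to Grade 3, in both places.

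As a clarification only, also add to the Grade 4 sentence: *and except immune-related ADRs managed per Table 7*. Keep this as an open reference. A closed list of skin and endocrine events would appear to exclude the hepatic Grade 3 to 4 row of Table 7, under which subjects with liver involvement at baseline may have treatment delayed and then resumed. Keep the permissive form of the opening clause and its Medical Monitor consultation: the Grade 3 to 4 skin row itself offers a choice between delay and discontinuation. Table 7 already bars resumption after toxic epidermal necrolysis or Stevens-Johnson syndrome, so no new text is needed there.

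The cost is a wording change or a clarification letter to sites, with no extra subjects or procedures.

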5.1.8 Analysis Cutoff Dates

After the end of the dose-escalation part of the trial, a full analysis for safety and PK / CCI data will be performed. The data cutoff date will be 6 weeks after the last subject of the escalation part has received his /her first administration of MSB0011359C. At the time of this amendment when adding the 2400 mg flat-dose cohort, the full analysis for the dose-escalation part of the trial had been completed. For the 2400 mg flat-dose cohort, an analysis will be performed at least 6 weeks after last subject first dose.

For the HCC ascending-dose cohort, an interim analysis will be conducted 12 weeks after the 30th subject in the 1200 mg ascending-dose portion received the first dose.

For the NSCLC anti-PD-1 / anti-PD-L1 failure cohort, an interim analysis will be conducted 12 weeks after the 40th subject in the cohort started treatment.

For the melanoma anti-PD-1 / anti-PD-L1 failure cohort, NSCLC second-line, pancreatic adenocarcinoma, CRC, TNBC, ovarian cancer, esophageal adenocarcinoma, SCCHN, glioblastoma, and cervical cancer cohorts, an interim analysis for that cohort will be conducted 12 weeks after the 30th subject in the cohort started treatment.

The primary data cutoff for the analysis of each expansion cohort separately will be 24 weeks after the last subject in that cohort started treatment (60th subject for the HCC cohort).

Final data cutoff will be after subjects are either enrolled into a roll-over trial or withdrawn after completing at least the Safety Follow-up visit at 10 Weeks (± 2 weeks) after Last Treatment (see Table 1).

